#### Secondary hypotheses and secondary endpoints

(S1) Worsening of MS-related disability is associated with loss of thalamus volume also if loss of whole brain volume is within the normal range.

Patients will be dichotomized with respect to the annual EDSS change during 24 months ('stable disability' versus 'progression of disability'), with respect to the annual change of thalamus volume ('stable thalamus volume' versus 'decline of thalamus volume'), and with respect to the annual change of brain parenchymal volume ('stable parenchymal volume' versus 'decline of parenchymal volume'). The parenchymal volume will be determined from the same T1w-MRI as the thalamus volume using a deep-learning based method developed and validated by JDX. The annual change of the parenchymal volume will be computed by linear regression of parenchymal volume versus time. Predefined cutoffs will be used for dichtomization. The association between dichotomized disability change and dichotomized thalamus volume change will be tested in the subgroup of patients with stable parenchymal volume using the chi-square statistic.

(S2) The change of thalamus volume during 24 months is predictive of the change of disability during the following 12 months (months 24-36).

EDSS will be determined at additional visits at 30 and 36 months. The annual change of EDSS between months 24 and 36 will be determined by linear regression of EDSS versus time including 24, 30 and 36 months. The annual change of EDSS between months 24 and 36 will be dichotomized using a predefined cutoff. The association between dichotomized disability change between 24 and 36 months and dichotomized thalamus volume change between baseline and 24 months will be tested using the chi-square statistic.

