## **Study Rationale**

The clinical course of multiple sclerosis (MS) is heterogeneous between patients and as of yet largely unpredictable on the single subject level. In addition to inflammatory demyelination and astrogliosis, neurodegeneration – a term that refers to structural axonal and neuronal damage plays a crucial role in the accrual of disability over time. An increasing body of evidence suggests that whole brain volume loss is indicative of disability progression (Sastre-Garriga et al. 2020). The mounting evidence prompted the MS community to add whole brain volume loss as a marker of tissue damage to the no-evidence-of-disease-activity (NEDA) concept. Since 2015 Germany-wide projects, such as QUANTUM, PANGAEA, MAGNON, have helped to establish a network of radiologists and neurologists for which accurate measurement and usage of whole brain volume loss (BVL) has become a "de-facto standard-of-care" (Schuh et al. 2020). Meanwhile, a solid connection between radiology centers, neurology centers and the investigator has developed. Through this network, thousands of MS patients in Germany recently received standardized MRI procedures for disease and therapy monitoring in routine clinical practice, providing hundreds of neurological centers in Germany with regular quantitative information on BVL and lesion activity.

The proposed study has the upside to build on this unique, large network and contribute to better understanding to what extent thalamus volume loss (TVL) appears as an independent driver of disability progression in early MS patients. Once proven and confirmed independently, TVL could serve as a potentially complementary marker of disease activity and a treatment target in future clinical practice, should surrogacy for disability progression be proven. Previous work has provided some important evidence rendering such ambitious goals within sight:

- 1. In the SUNBEAM and RADIANCE phase III trials, MS patients in the OZANIMOD groups showed a significant slowing of cortical gray matter and thalamic volume loss as compared to an active comparator (Cohen et al. 2019; Comi et al. 2019).

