## **Secondary objectives:**

# (S1) To demonstrate that worsening of MS-related disability is associated with loss of thalamus volume also if loss of whole brain volume is within the normal range.

Based on the individual results for TVL and BVL derived from three routine MRIs, the study population will be divided into four distinct subgroups as suggested by Opfer et al. (2020) and shown in Figure 4.

**Figure 4.** Clinical characteristics of group 2 ( $\sim$ 25% of all patients) are of particular interest and whether group 2 is statistically distinct with regard to clinical and imaging data.

The probable frequencies for these groups were also taken from this paper:

**Group 1**: normal BVL, normal TVL (estimated frequency ~50% of the total relapsing-remitting MS population); **Group 2**: normal BVL, pathological TVL (~25%); **Group 3**: pathological BVL, pathological TVL (~25%); **Group 4**: normal TVL, pathological BVL (~0%)

We will use the cut-offs for normal and pathological TVL presented in Opfer et al. (2020) and corresponding cut-offs for BVL as published in Opfer et al. (2018a and 2018b).

At month 24 study subjects shall be grouped based on their individual EDSS increase in patients with (confirmed) disability progression and patients without disability progression.

Dichotomization is based on the following cut-offs:

**Group A** (with evidence of disability progression / confirmed disability progression)

- −1.0 increase for study subjects with baseline EDSS scores from 1.0 to 5.0
- −0.5 increase for study subjects with baseline EDSS scores equal or higher than 5.5

**Group B** (no evidence of disability progression)

We will perform a chi-square test to see if there is a significant difference between the frequency of patients with progressive disability (group A) and without evidence of progressive disability (group B).

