#### 5. STUDY LIMITATIONS/STRENGTHS

#### Generalizability of study results

The PENTAGON study if pursued over the full length is able to link results of the phase III clinical trials (RADIANCE and SUNBEAM) regarding the effect of ozanimod on brain volume, and in particular TVL to disability progression in a real world setting. Once confirmed pathological TVL could be considered an independent risk factor for disability worsening. This would then justify inclusion of TVL into the spectrum of treatment targets in MS.

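### S1 tests association within normal whole-brain loss, but its single-cut-off control cannot carry the reading that thalamic loss is an independent risk factor

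*Protocol*

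**What the plan says.** Protocol section 3 (Secondary hypotheses and secondary endpoints) states the S1 hypothesis: "Worsening of MS-related disability is associated with loss of thalamus volume also if loss of whole brain volume is within the normal range". EDSS change, thalamus volume change and parenchymal volume change are each split at predefined cut-offs. The association of the first two "will be tested in the subgroup of patients with stable parenchymal volume using the chi-square statistic".

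Section 4 (S1) forms four groups with expected shares:

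- Group 1, both losses normal: about 50%.
- Group 2, normal BVL with pathological TVL: about 25%.
- Group 3, both pathological: about 25%.
- Group 4, normal TVL with pathological BVL: about 0%.

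The covariate table in section 3 lists intracranial volume, age, sex, disease duration, baseline lesion parameters, baseline EDSS and treatment. It does not list BVL. Section 5 (Bias/confounding and effect modification) offers only treatment as a covariate. BVL enters a multivariable model only in S2, whose outcome is progression in months 24–36 and which depends on the optional extension.

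On interpretation, section 1 (Study Rationale) says the study should help show to what extent "thalamus volume loss (TVL) appears as an independent driver of disability progression". Section 5 (Generalizability of study results) says: "Once confirmed pathological TVL could be considered an independent risk factor for disability worsening", and presents this as grounds for making TVL a treatment target.

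**The concern.** Restricting to one side of a cut-off removes the patients with large BVL but leaves BVL varying among those who remain. If TVL group still tracks BVL in that remainder, and BVL relates to disability, groups 1 and 2 will differ in progression even when TVL adds nothing at a given BVL.

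The protocol itself points to both conditions. Section 1 treats whole-brain loss as indicative of progression, and the group shares place nearly every patient with pathological BVL among those with pathological TVL. S1 is the only analysis of the month-24 outcome that deals with BVL at all, so a positive S1 is the natural support for the word independent. It would then carry a claim that the test does not examine.

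**Working it through.** **1. The plan's own figure.** Section 4 (Power/Sample Size) gives 196 and 98 for 5% against 15%, type I error 0.05 and type II error 0.20. With a two-sided test, 2:1 allocation, no continuity correction and p̄ = (2 × 0.05 + 0.15)/3 = 0.0833:

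n₁ = [1.960 × √(3 × 0.0833 × 0.9167) + 0.842 × √(0.05 × 0.95 + 0.15 × 0.85/0.5)]² / 0.10² = (0.938 + 0.463)²/0.01 ≈ 196.3.

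This agrees with 196/98. The total is (196 + 98)/0.75 = 392, as in the attrition table. The sample size is not in question.

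**2. What the shares imply.** The proportion with pathological TVL is 25/25 = 100% when BVL is pathological and 25/75 = 33% when BVL is normal. The phi coefficient is (0.25 − 0.50 × 0.25)/√(0.5 × 0.5 × 0.25 × 0.75) = 0.58, the largest these margins allow.

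**3. From shares to a correlation (assumption: bivariate normal).** BVL severity B is cut at its 75th percentile and TVL severity T at its median. The TVL–BVL correlation r that produces a given group 4 share is:

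| Group 4 share | 0.5% | 1% | 2% | 3% |
|---|---|---|---|---|
| r | 0.90 | 0.86 | 0.79 | 0.72 |

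Inside the normal-BVL range, group 2 then averages 0.91 SD more BVL than group 1 at r = 0.90 and 0.64 SD more at r = 0.70. At r = 0.50 the gap is about 0.45 SD.

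**4. Rejection when TVL has no effect at a given BVL.** The progression liability is L = ρB + √(1 − ρ²)ε, with 10% overall progression (assumed), N = 392 and the uncorrected chi-square in the normal-BVL subgroup. Section 4 says the published correlation between disability change and whole-brain change is of the same order as 0.15. Applying that value on the liability scale is a further assumption, and ρ = 0.30 is purely an assumption. Results from 6,000 simulated trials (r = 0.50: 5,000 trials, ρ = 0.15 only):

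| r | ρ = 0 | ρ = 0.15 | ρ = 0.30 |
|---|---|---|---|
| 0.50 | – | 6.1% | – |
| 0.70 | 4.7% | 7.6% | 13.3% |
| 0.85 | 4.9% | 10.4% | 20.1% |
| 0.90 | 5.2% | 9.8% | 22.9% |

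Separate runs at ρ = 0.15 gave 6.9% and 8.3% at r = 0.70, and 10.2% and 9.7% at r = 0.90, so the spread between runs is small. At r = 0.90 and ρ = 0.15, BVL alone produces about 8.2% against 10.2% progression. That 2-point gap compares with the 10 points S1 is powered for.

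**5. A second model.** Here progression is logistic in BVL, calibrated to the protocol's average of 8.33% in groups 1 and 2, with exact enumeration at 196/98. At r = 0.9 rejection is 9% for an odds ratio of 1.3 per SD of BVL (latent correlation about 0.13) and 14% for 1.5 (about 0.20). At r = 0.5 it is 6% and 7%. The direction and order of size agree with step 4.

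**6. With BVL adjusted.** Adding continuous BVL to a logistic model in the same subgroup returns the rejection rate for TVL group to 5.2% (ρ = 0.15) and 5.4% (ρ = 0.30) at r = 0.90. For a true TVL-group effect of 5% against 15%, power is about 0.59–0.67, against 0.79–0.85 for the chi-square. These simulations take BVL as measured without error.

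**The case against.** The strongest reply is that S1 tests exactly what it states. If group 2 progresses more often than group 1 among patients with normal BVL, the hypothesis is true as worded, whatever the mechanism. That stands. A reader might infer from the table that S1 has an inflated type I error. The documents do not support that, because the rates above 5% are measured against a null hypothesis (no TVL effect at the same BVL) that S1 does not state.

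A reader might also infer that the protocol commits itself to calling TVL independent once S1 rejects. It does not. The section 5 sentence is conditional and does not name S1. The parallel sentences in the synopsis and at the end of the Study Rationale speak of a risk factor without that adjective. No decision rule links the two.

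The size is also open to challenge. The TVL–BVL correlation is inferred from approximate shares under an assumed distribution. The scatter plot that could show it is not available here, and section 1 stresses that the two losses can diverge. A rejection rate of four to five times 5% needs ρ = 0.30, which the documents do not give. With a continuity correction, which the protocol neither specifies nor excludes, the rate at ρ = 0.15 is only about 6%.

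Finally, the statistical analysis plan is not at hand and could add an adjusted model. That limits the point but does not remove it: the protocol itself fixes the unadjusted test, leaves BVL off its covariate list, and states the independent reading.

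**Conclusion.** The point holds as one of interpretation. S1 is a valid test of association within normal BVL, but it cannot by itself support the independent reading in sections 1 and 5, because a single cut-off leaves BVL differences between groups 1 and 2 and no analysis of the month-24 outcome adjusts for them.

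At the only anchor the protocol gives, the consequence is modest: about 7–10% rejection from BVL alone for TVL–BVL correlations of 0.7–0.9, and about 6% at 0.5. The 13–23% range applies only at an assumed BVL–disability correlation of 0.30. All these figures rest on bivariate normality, a group 4 share read as 0.5–3% for the upper correlations, 10% overall progression, and an uncorrected chi-square. The change is worth making because the gap between test and claim is plain and closing it is cheap.

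**What to change.** 1. Keep the S1 chi-square, its subgroup and its sample size.
2. Add to section 4 (S1) a supportive logistic regression in the same normal-BVL subgroup: progression on TVL group, with annual BVL as a continuous covariate. Add BVL to the covariate table in section 3.
3. In section 4 (S1) and section 5 (Generalizability of study results), state that TVL is called independent only if the BVL-adjusted TVL effect is significant. Otherwise the conclusion reads: associated within the normal range of whole-brain loss.

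The cost is one more model on data already collected, plus a claim that is harder to reach given the lower adjusted power. Two limits should be stated with the result. The thalamus is part of whole-brain volume, so the adjustment may remove some real thalamic signal. BVL is also measured with error, so it may not remove all confounding. If the sponsor does not want the extra model, softening the section 1 and section 5 wording would by itself remove the overstatement.

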## Exposure/Independent Variables of Interest

Not applicable

#### Other Co-variates/Control Variables

| Total intracranial volume (TIV) | most regions-of-interest (such as the thalamus) in the brain, MRI-based     |
|---------------------------------|---|
|                                 | volume estimates are associated with TIV. Careful adjustment for TIV is     |
|                                 | required to improve the statistical power and to avoid spurious effects and |
|                                 | misinterpretation of actual effects.  |
|                                 | -   |

| Age and sex   | Regional brain volumes are strongly correlated with age and sex.   |
|---|--|
| Disease duration  | EDSS and MRI-based volume estimates are associated with disease duration (time since diagnosis). Treatment may affect TVL, new lesions, and disability worsening. Mitigation may be to use treatment as a covariate in statistical analysis.   |
| Baseline parameters used to
define inclusion, such as T2
lesion load, Gd-enhancing
lesions, new/enlarging T2 lesions | All these parameters could have a confounding effect and are thus to be controlled.  |
| EDSS at baseline  | EDSS at baseline is also a predictor for disability progression and should be controlled.  |
| Treatment regimen   | EDSS and MRI-based volume estimates are associated with disease duration.  Treatment may affect TVL, new lesions, and disability worsening.  Mitigation may be to use treatment as a covariate in statistical analysis.  Treatments are first-line oral immune therapies such as teriflunomide, ozanimod, dimethylfumarate, ponesimod, and diroximethylfumarate. |

#### 4. STATISTICAL ANALYSIS

#### **Statistical Analysis Methods**

In the following the statistical analysis methods to be used are discussed:

# Primary objective: To demonstrate that the change of MS-related disability during a period of 24 months is inversely associated with change of thalamus volume during the same period.

In a previous project sponsored by Celgene, the investigators in this study developed and validated a technique that allows reliable and robust calculation of change in regional volumes based on a longitudinal approach in high-resolution T1w MRIs (Opfer et al. 2020). Such an approach allows percentage estimation of volume change of corresponding regions in successive high-resolution T1w MRIs and is much less susceptible to noise than conventional methods based on calculation of absolute volumes at different time points and a regression model to estimate volume change. It has the potential to overcome the technological limitations that hindered the work of Eshaghi et al. (2018).

[figure not shown]

Figure 3. Linear regression of all EDSS measurements

With this approach, it is methodologically feasible to assess TVL and deep GMVL for individual MS patients.

MS-related disability will be characterized by the Expanded Disability Status Scale (EDSS). The EDSS will be determined at inclusion (baseline), at 24 months after inclusion, and at additional visits at time intervals approx. every 6 months in between. The annual change of EDSS during the 24 months' period will be computed by linear regression of EDSS versus time including all visits (Fig. 3). The slope of the regression line will be the annual change of EDSS.

[figure not shown]
For the correlation analysis annual change of EDSS and annualized TVL will be considered as continuous variables. For all study subjects three high-resolution T1w-MRI scans will available. TVL will be calculated for each pair of two consecutive MRI scans. Annualized TVL between the baseline (BL) and last follow-up (FU) scan will be calculated by multiplying the TVL between the two consecutive scans and dividing the resulting TVL with the time interval between BL and FU scan.

A Pearson correlation analysis will be used to test for with a significance level of p = 0.05. Outcomes can be modelled both as dichotomous (CDP – yes, no) and continuous (raw EDSS score) variables. In case of dichotomous variables, a logistic regression will be used.

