#### **Data Analyses:**

The year-to-year change in EDSS during the 24-month period is calculated by linear regression of EDSS against time, accounting for all visits. The slope of the regression line is the annual change in EDSS. For the correlation analysis, the annual change in EDSS and annualized TVL are considered continuous variables. Three high-resolution T1w MRI scans will be available for all study participants. TVL will be calculated for each pair of two consecutive MRI scans using an advanced and validated method from Opfer et al (2020) that is less susceptible to noise and therefore can estimate TVL in individual subjects. The annualized TVL between the baseline scan (BL) and the last follow-up scan (FU) is calculated by multiplying the TVL between the 2 consecutive scans and dividing the resulting TVL by the time interval between the BL and FU scans. A Pearson correlation analysis is used to test for a significance level of p = 0.05.

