## Outcomes/Endpoint Variables

Primary hypothesis and primary endpoint

The change of MS-related disability during a period of 24 months is inversely associated with the change of thalamus volume during the same period.

MS-related disability will be characterized by the Expanded Disability Status Scale (EDSS). The EDSS will be determined at inclusion (baseline), at 24 months after inclusion, and at additional visits at time intervals approx. every 6 months in between. The annual change of EDSS during the 24-month time period will be computed by linear regression of EDSS versus time including all visits. The change of thalamus volume will be determined in consecutive high-resolution T1w-MRI using a deep-learning based method developed and validated by JDX (Opfer et al. 2020). TVL will be calculated for each pair of two consecutive MRI scans using an advanced and validated method from Opfer et al (2020). The primary endpoint is the Pearson coefficient of the correlation between the annual change of EDSS and the annual change of the thalamus volume.

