#### Secondary data analysis

The investigators have access to a large brain MRI database of MS patients sampled over the past 3 to 4 years from multiple centers across Germany. We will select MS patients from the brain MRI database whose data match best the requirements of the prospective observational study. Since EDSS scores are sparsely available, missing clinical data will be retrospectively collected by the investigators from the associated neurology centers. Then, we will compare three alternative methods to measure TVL and associations with change in EDSS: The Jacobian method as described in (Opfer et al. 2020) uses a longitudinal registration technique which is based on a pairwise inverse-consistent highly elastic diffeomorphic alignment of baseline (BL) and the follow-up (FU) scans to the halfway image space of the subject. The approach incorporates rigid registration into a halfway image space (an image space between BL and FU image) and correction for intensity inhomogeneities. The output Jacobian is the composition of two Jacobians: the Jacobian of the transformation field from the halfway space image to the FU scan and the negative Jacobian from the halfway image to the BL scan. Each voxel of the Jacobian therefore describes the percentage volumetric change between BL and FU image for that particular voxel location. To estimate the volumetric change of certain subregions of the brain the signal of the Jacobian needs to be integrated over a region of interest. The above approach is based on an elastic registration of the whole brain image. As an alternative technique the above approach will be deployed for a region around the structure of interest (ROI) (the thalamus for example). The two images will be registered into a halfway space. In both images a bounding box around the ROI will be extracted from the whole image. The above-described steps will be performed using the bounding boxes instead of the whole brain image. The third approach uses a segmentation of the ROI in the baseline image. The highly elastic diffeomorphic registration will be used to compute a displacement field of the boundary of the ROI. From the displacement fields at the boundary a volume change can be determined. The three methods will be compared with respect to stability and sensitivity using the cohorts and methods described in Opfer et al. (2020). The most suitable method will qualify for application to the primary data. Important conclusions regarding the statistical design can be drawn from the results.

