#### **Power/Sample Size**

#### Primary objective

We want to show whether the correlation between the change in MS-related disability and the change in thalamic volume is different from zero. Both the change in MS-related disability and the change in thalamic volume are continuous variables. We will use Pearson's correlation analysis. The expected correlation coefficient is 0.15, which seems to be a reasonable assumption at this point because the correlation coefficient between change in MS-related disability and change in total brain volume published recently by Uher et al. (2021) is of the same order of magnitude.

Assuming a type I error of 0.05 and a type II error of 0.20, we estimate the required sample size to be 347 (24 months after baseline EDSS measurement). Considering an annual dropout rate of 15% the total required sample size is approximately 600 study participants.

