#### Missing data handling

Three MRIs will be available per patient. TVL will be calculated for each pair of two consecutive MRI scans. Annualized TVL between the baseline (BL) and last follow-up (FU) scan will be calculated by multiplying the TVL between the two consecutive scans and dividing the resulting

TVL with the time interval between BL and FU scan. If for a patient only two MRIs are available, the TVL can still be computed in the same way. If only one MRI is available, TVL cannot be computed, and the patient will be excluded from the study.

As explained above EDSS scores will be measured approximately every 6 months. The annual change of EDSS during the 24 months' time period will be computed by linear regression of EDSS versus time including all visits (see Fig. 3). This approach still works if EDSS measurements are missing. At least two EDSS measurement are needed otherwise the patient needs to be excluded from the study.

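### The written formula for annualized thalamus volume loss multiplies percentage changes and divides by time, which does not give an annual change in a primary-endpoint variable

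*Protocol*

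**What the plan says.** Section 4, Statistical Analysis Methods (primary objective) has TVL computed per scan pair: "TVL will be calculated for each pair of two consecutive MRI scans". The annualized value from baseline (BL) to the last follow-up scan (FU) is then "calculated by multiplying the TVL between the two consecutive scans and dividing the resulting TVL with the time interval between BL and FU scan". The Synopsis, under Data Analyses, gives the same rule in slightly different words: "calculated by multiplying the TVL between the 2 consecutive scans and dividing the resulting TVL by the time interval between the BL and FU scans". Missing data handling repeats it and adds: "If for a patient only two MRIs are available, the TVL can still be computed in the same way".

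The protocol describes the interval measure as a percentage change. Section 4 says of the method: "Such an approach allows percentage estimation of volume change of corresponding regions in successive high-resolution T1w MRIs". The Secondary data analysis text says of its output: "Each voxel of the Jacobian therefore describes the percentage volumetric change between BL and FU image for that particular voxel location". No section adds 1 before the multiplication or subtracts 1 after it.

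Under Outcomes/Endpoint Variables: "The primary endpoint is the Pearson coefficient of the correlation between the annual change of EDSS and the annual change of the thalamus volume". Under Power/Sample Size: "The expected correlation coefficient is 0.15", with a type I error of 0.05, a type II error of 0.20 and n = 347.

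**The concern.** Percentage changes over successive intervals can be compounded as volume ratios or, when small, added. Multiplying the changes themselves gives a quantity in squared percent. It does not rise steadily with loss, and it cannot tell two losses from two gains. Dividing it by time does not turn it into an annual rate.

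The result is one of the two variables in the primary correlation. An analyst who follows the protocol to the letter would correlate EDSS slope with something other than the annual change of thalamus volume that the endpoint names. An analyst who corrects the rule silently would depart from the protocol on its main variable. Because the rule appears three times, once in different words, it is unlikely to be an isolated slip of the pen.

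**Working it through.** **The plan's own figure.** Fisher z, two-sided: n = ((1.960 + 0.842) / atanh(0.15))² + 3 = 346.6, so 347, as stated. A one-sided test would need 274. This figure depends only on r, alpha and power, so the formula problem does not change it.

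**The formula as written.** Example interval changes over T = 2 years, comparing the literal product TVL1 x TVL2 / T (in percent units) with the compounded value [(1 + TVL1/100)(1 + TVL2/100) - 1] x 100 / T:

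| TVL1, TVL2 | Literal (%²/yr) | Compounded (%/yr) |
|---|---|---|
| -1%, -1% | +0.5 | -0.995 |
| +1%, +1% | +0.5 | +1.005 |
| -2%, 0% | 0 | -1.000 |
| -0.5%, -1.5% | +0.375 | -0.996 |
| -2%, -2% | +2.0 | -1.980 |

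Loss and gain coincide (rows 1 and 2). A zero interval erases the other interval's loss (row 3). Nearly equal total losses give different values (rows 1 and 4). Doubling both losses quadruples the result (rows 1 and 5).

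**TVL read as a volume ratio.** The product 0.99 x 0.99 = 0.9801 is the right total ratio. Dividing it by 2 without first subtracting 1 gives 0.49, which is not an annual loss and varies mainly with 1/T.

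**Two-scan patients.** They have one TVL and nothing to multiply. Their value is TVL/T in %/yr, while three-scan patients are in %²/yr, within the same correlation.

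**Possible size (illustration only).** The protocol gives no TVL distribution. Assume a mean annual change m of -0.3% to -1.5%, between-patient SD s of 0.6 to 1.0, interval noise SD e of 0.4 to 0.8, and |r| = 0.15 for the correctly annualized variable. Let V = s² + e² and C = s². For normal variables the correlation of the product with the sum of the two changes is m√(2(V+C)) / √(2m²(V+C) + V² + C²). The sum and the compounded version correlate above 0.9999.

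- m = -0.3, s = 1.0, e = 0.8: V = 1.64, C = 1. Magnitude 0.3 x 2.298 / 2.041 = 0.338, so |r| = 0.15 x 0.338 = 0.051.
- m = -1.5, s = 0.6, e = 0.4: V = 0.52, C = 0.36. Magnitude 1.5 x 1.327 / 2.088 = 0.953, so |r| = 0.15 x 0.953 = 0.143.

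Power is Φ(atanh|r| x √344 - 1.960), which gives about 15% and 76% at these two ends. Simulation over the same grid gives |r| of about 0.05 to 0.14 and power of about 14% to 76%.

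For the ratio reading, a total-interval SD of 0.5 to 1 month is a further assumption. The spread due to T alone is 0.49 x SD(T)/2 years: 1.02 percentage points at 0.5 month and 2.04 at 1 month. The spread due to true change is √(4s² + 2e²)/2: 0.66 at the low end and 1.15 at the high end. Then |r| = 0.15 x 0.66/√(0.66² + 2.04²) = 0.046 and 0.15 x 1.15/√(1.15² + 1.02²) = 0.112. Simulation gives about 0.045 to 0.115, with power of about 13% to 56%. The ends shift somewhat with how loss over unequal intervals is modelled.

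**The case against.** The strongest reply is that this is loose wording for compounding. The text calls the product a TVL from baseline to last follow-up, which is what chaining volume ratios would give, and the endpoint itself is named correctly as an annual change. Under compounding, one interval is simply one factor, so the two-scan sentence would be right. Nothing in the protocol shows that the software computes the literal product, and an analysis plan not seen here may hold the correct formula. All of this is fair, and compounding is the likely intention. It does not repair the text: no section states the conversion, and this is an explicit rule, not a detail left open for later. The composition of Jacobians under Secondary data analysis describes the halfway registration within one scan pair, not the chaining of two intervals.

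Three stronger readings may tempt a reader, and the protocol does not support them.

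- **The primary test would come out with the wrong sign.** That holds only if loss is coded negative. TVL is named as a loss, the expected coefficient is given as a positive 0.15, and no coding is fixed. With loss coded positive, the literal product is attenuated but points the same way.
- **The error carries into S1 and S2.** Section 4 introduces the formula for the correlation analysis, and S1 applies published cut-offs. Missing data handling restates the formula without limiting it, so reuse is plausible, but it is not stated.
- **Mixing two-scan and three-scan patients has a definite effect on r.** The result depends on the unit: with 5% to 20% two-scan patients (assumed) and loss coded negative, r is about -0.01 to -0.06 with TVL as a fraction and about 0.00 to +0.12 in percent. The protocol fixes neither the unit nor the share, so no single figure can be given.

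**Conclusion.** The written rule is wrong under either reading of TVL and must be corrected before analysis, because it defines one of the two variables in the primary endpoint. This conclusion needs no assumption about the data.

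The size of the effect does need assumptions. Under those set out above, literal use would cut power from 80% to about 14% to 76%, with the largest loss when mean atrophy is small. At a mean of -1.5% per year power stays near 70% or above. Under the ratio reading it would be about 13% to 56%. These are illustrations of what following the text could cost. They do not show that the primary test will fail, since the protocol does not reveal what the software computes.

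**What to change.** In the Synopsis (Data Analyses), Section 4 (primary objective) and Missing data handling, replace the sentence with:

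annualized TVL (%/yr) = [product over consecutive scan pairs of (1 + TVL_i/100) - 1] x 100 / (years from BL to last usable FU),

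where TVL_i is the signed percentage change over pair i, with loss negative. For a patient with two scans the product has one factor, so the value is TVL_1 / years. With this coding the hypothesized inverse association is a negative correlation, and the 0.15 in the sample-size section should be labelled as its magnitude. State also whether the same variable is used for the TVL classification in S1 and S2.

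The cost is one formula in three places and two clarifying sentences. No further data are needed, and n = 347 stays as it is.
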